**Proprietary confidential information.**

© 2015 Boehringer Ingelheim International GmbH or one or more of its affiliated companies. All rights reserved.

This document may not - in full or in part - be passed on, reproduced, published or otherwise used without prior written permission.

10. Treatment with sulphonylureas, thiazolidinediones, **meglitinides, bromocriptine**, SGLT2 inhibitors, or DPP-4 inhibitors within 3 months prior to randomization (Visit 3).
11. Treatment with rapid acting or short acting insulin and/or pre-mixed insulin containing rapid acting or short acting insulin within 3 months prior to randomization (Visit 3).
12. Known hypersensitivity, allergy, or any contraindication to linagliptin or its excipients or the patients' background therapy (i.e., basal insulin, metformin, or alpha-glucosidase inhibitors) or placebo, according to local labels.
13. Treatment with anti-obesity drugs, including over-the-counter drugs such as Alli® (orlistat), 4 weeks prior to informed consent or any other treatment at the time of screening (i.e., surgery, aggressive diet regimen, etc.) leading to unstable body weight.
14. Current treatment with any drugs known to have significant effect on glucose metabolism, such as systemic steroids, at time of informed consent or change in dosage of thyroid hormones within 6 weeks prior to informed consent or any other uncontrolled endocrine disorder excluding T2DM.
15. Alcohol or drug abuse within the 3 months prior to informed consent that would interfere with trial participation or any ongoing condition leading to decreased compliance to trial procedures or study medication intake in the opinion of the investigator.
16. Participation in another trial with an investigational drug within 2 months prior to informed consent.
17. Psychological, familial, sociological, or geographical factors potentially hampering compliance with the protocol, visits, or trial procedures or any other clinical condition that would jeopardize patient safety while participating in this clinical trial in the opinion of the investigator.
18. Inability to commit to regular overnight fasting of at least 10 hours duration and attendance to trial site visits between 07:00 and 11:00 ante meridiem (a.m.).

NOTE: No protocol waivers will be granted for any reason during the trial. Patients who do not meet one or more of the entry criteria or discontinue before Visit 3 will not be randomised and will be screen failures. The primary reason for the screen failure will be recorded on the electronic case report form (eCRF).

If a protocol violation occurred in relation to inclusion or exclusion criteria and a patient was mistakenly randomized, the investigator will need to contact the CML to request permission for the patient to continue in the trial, document the reason for this protocol violation in the patient's medical records, and report the protocol violation to their Institutional Review Board (IRB) or Independent Ethics Committee (IEC).

### 3.3.4 Removal of patients from therapy or assessments

#### 3.3.4.1 Removal of individual patients

##### Screen failures

Patients who do not meet one or more of the entry criteria or discontinue before Visit 3 will not be randomized and will be screen failures. The primary reason for the screen failure will be recorded on the eCRF. Patients who have screen failed in this trial are not permitted to be re-screened at a later time point.

##### Discontinuing or withdrawing patients from the trial

If a patient discontinues (drops out or withdraws) from this trial after randomization, the patient will not be replaced.

Patients have the right to withdraw from this trial at any time for any reason. The patients will be asked by the investigator to provide the specific reason for their withdrawal from the trial (e.g., moving out of the state or country, unable to drive to trial site, etc.) and this reason will be recorded on the eCRF.

Patients who discontinue from this trial are not allowed to re-enrol in this trial, including patients from other trial sites.

Patients will be discontinued from the trial for:

- significant non-compliance (If the patient fails to comply with the protocol (e.g., non-compliance with study medication or evaluations), a patient may be discontinued after discussion between investigator and sponsor),
- concomitant drugs that interfere with the medications being given in this trial,
- no longer being able to participate for other medical reasons (e.g., surgery, AEs, or other diseases),
- persistent hyperglycaemia that is uncontrolled with rescue medication as described in [Section 4.2.1](#) (In this case, the reason for discontinuation will be classified as “lack of efficacy”), and
- occurrence of hypoglycaemia that may put the patient at risk with continued participation (e.g., repeated hypoglycaemic episodes).
- If pancreatitis is suspected, the study medication should be stopped.

The investigator also has the right to withdraw patients from the trial because continuation of study medication or continuation of the follow up visits may not be in the best interest of the patient.

If necessary for patient safety, as determined by investigator, new antidiabetic medication regimen may be started the day after study medication discontinuation. The new antidiabetic medication must be recorded in eCRFs.

**Proprietary confidential information.**

© 2015 Boehringer Ingelheim International GmbH or one or more of its affiliated companies. All rights reserved.

This document may not - in full or in part - be passed on, reproduced, published or otherwise used without prior written permission.

It is understood by all concerned that an excessive rate of withdrawals can render the trial uninterpretable; therefore, unnecessary withdrawal of patients should be avoided. Should a patient decide to discontinue, all efforts by the investigator will be made to complete and report the last treatment visit evaluations (i.e., Visit 98) as thoroughly as possible.

If a patient discontinues from this trial, the patient should have the Visit 98 (the final assessment that is considered to be on-treatment or shortly thereafter) evaluations completed as soon after stopping study medication as possible. Additionally, the patient should have the Post-Treatment Visit (Visit 99) evaluations completed one week after Visit 98. The investigator or a staff member should contact the patient (or a responsible relative or designee) either by telephone to determine the primary reason for withdrawal from the trial if the patient refuses to return to the trial site. The primary reason for the withdrawal from the trial will be recorded on the Termination of Trial Medication eCRF. If the patient is dropped due to an adverse event, the Termination of Trial Medication form must agree with the adverse event eCRF. The reason for discontinuation will be included in the trial database and reported.

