#### 4.1.4 Drug assignment and administration of doses for each patient

Patients will continue with the permitted antidiabetic therapy throughout the duration of the trial unless a medical emergency or another plausible reason (e.g., renal impairment, lactic acidosis, dose intolerance, hypoglycaemia, or hyperglycaemia) necessitate changes (at the discretion of the investigator). If a patient is taking antidiabetic therapy that includes metformin and is expected to be exposed to an iodine-containing contrast agent for a diagnostic or surgical procedure, metformin should be temporarily stopped before and after the administration of iodine-containing contrast agent according to the metformin prescribing information and regional or local guidelines.

Patients who qualify for double-blind treatment will be randomized to one of the dosage and treatment schedules described in Table 4.1.4: 1. The study medication for this trial will be dispensed in a double-blind manner. Each patient will receive a Run-In bottle at Visit 2 and be instructed to take placebo medication daily for one week. At Visit 3, patients who qualify based on inclusion and exclusion criteria will be randomised to one of the two dosage regimens, either linagliptin 5 mg daily or placebo matching linagliptin daily.

Dispensing of bottles for the double-blind treatment period will begin at Visit 3. Dispensing will occur on 4 occasions over a period of 24 weeks. For further details regarding packaging (e.g., number of tablets per bottle), refer to [Section 4.1.6](#).

Table 4.1.4: 1 Treatment group dosing schedule

Group 1: linagliptin 5 mg treatment group

Visit	Day	Treatment arm	Morning	Note
2	-7	placebo	○	Run-In Period
3 to 98	1 to 169	linagliptin 5 mg	●	Treatment Period: The last dose of study medication will be taken by the patient on the morning before Visit 98.

●: linagliptin 5 mg tablet; ○: placebo for linagliptin 5 mg tablet

Group 2: placebo for linagliptin 5 mg tablet treatment group

Visit	Day	Treatment arm	Morning	Note
2	-7	placebo	○	Run-In Period
3 to 98	1 to 169	placebo for linagliptin 5 mg	○	Treatment Period: The last dose of study medication will be taken by the patient on the morning before Visit 98.

○: placebo for linagliptin 5 mg tablet

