#### Post-Treatment Period

Patients that complete the trial will take the last dose of study medication the day before Visit 98. The investigator may initiate any additional antidiabetic therapy based on his or her discretion no sooner than one day after Visit 98.

The following Visit 99 evaluations should be performed for all patients returning for this visit including those patients who prematurely discontinued from the trial:

- Blood pressure and pulse
- Collection of blood and urine samples for safety laboratory evaluation
- Return of the HBGM device for assessment of blood glucose levels
- Return of the eDiary
- Documentation of any adverse events
- Documentation of concomitant therapies

The end of the trial is defined as "last patient out", i.e., last visit completed by the last patient.

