Missing safety data will not be replaced, but an analysis of the changes from baseline to the last available value under treatment and the minimum and maximum post baseline will be determined for quantitative safety laboratory variables. For safety analysis, as last on-treatment value the last measurement between the first intake of randomised trial drug and drug-stop date + 7 days will be analysed as the last value on-treatment for non-Japanese patients. If a Japanese patient stops drug intake prior or at day 175 a residual period of 7 days will be added for Week 24 safety analysis. If a Japanese patient does not stop drug intake prior day 176, no residual period is added for safety analysis.

Missing dates and times

Missing or partial date and time information for adverse events (AEs) will be replaced according to general Boehringer Ingelheim (BI) rules (cf. [1](#)).

If the date of first drug administration is missing but the patient was randomised and treated, the date of the first drug administration will be set to the date of randomisation.

If the date of first administration is partially missing with the month and year present, the day will be set to the date of randomisation if randomisation was in the same month. If randomisation was in the month prior to the first drug administration the missing day will be imputed as the first day of the month.

A missing time of first drug administration will be imputed as 12:00 o'clock noon, missing administration times at on-treatment visits will be imputed by 8:00 o'clock in the morning.

As a general rule, a missing drug stop date will be imputed according to the following principles:

- If an End of Treatment (EoT) visit is documented, it should be the date of the EoT visit (Visit 98).
- If the date is incomplete with only month and year and the EoT visit is missing, it should be the first day of the following month.
- If the patient is lost to follow-up it should be the date of the last visit + the longest treatment duration based on drug supply + 1 day.
- All other cases need to be assessed by the trial team on an individual basis, trying to use the points above as guidance.
- After application of any of the first 3 rules, the post-treatment phase starts at the same day as the imputed drug stop date (instead of treatment stop + 1 day).

If only the year of birth is known, the day and month of birth will be imputed as 01 January. If month and year are known, the day of the birth will be imputed as 01.

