6.7 BASELINE, TIME WINDOWS AND CALCULATED VISITS

Definition of baseline

With regard to efficacy and safety endpoints, the term "baseline" generally refers to the last observed measurement prior to administration of any randomised study medication. Baseline daily basal insulin dose is derived from eCRF and is equal to the daily basal insulin dose at day of first study medication intake. If patients are treated by a combination of a fast-acting and basal insulin, only the proportion of basal insulin is used for deriving the baseline daily basal insulin dose. If that proportion cannot be derived, baseline daily basal insulin is set to missing.

If patients are treated with an intermediate type of insulin, then this dose is completely considered for daily basal dose.

Also, for metformin and AGI, baseline doses refer to the dose at day of first study medication intake.

Measurements taken prior to the first intake of randomised trial medication will be considered pre-treatment values. These pre-treatment values will be assigned to a visit according to the nominal visit number as recorded on the eCRF or as provided by the laboratory.

The date and clock time of the first study medication administration will be used to separate pre-treatment from on-treatment values.

The definition of screening for the analysis of concomitant therapies (CTs) is the time period from informed consent up to the first dose of trial medication.

Definition of on-treatment for analyses

Measurements taken after the first intake of randomised study medication will be considered on-treatment values if they have been obtained up to 7 days after study medication stop (inclusive) – this also holds for hypoglycaemia (efficacy endpoints) and hypoglycaemic adverse events (safety endpoints). The only exceptions are FPG [REDACTED] for which will be up to 1 day after drug stop (inclusive) due to reacting quicker. All on-treatment measurements will be assigned to the randomised trial medication for analyses.

Measurements taken after the end of the follow-up period after the last intake of trial medication will be considered post-trial values.

Visit windows for efficacy variables

On-treatment efficacy measurements will be assigned to visits based on time windows around the planned visit dates. These time windows are defined based on the planned number of days after the date of first administration of trial medication (this is at Visit 3).

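### SAP 6.6 imputes a missing drug stop date as the Visit 98 date, so an early stopper's off-drug FPG (gap of 2 days or more) or HbA1c (8 days or more) can count as on-treatment

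*Protocol*

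**What the plan says.** **Last dose relative to Visit 98.** Protocol Table 4.1.4: 1 states: "The last dose of study medication will be taken by the patient on the morning before Visit 98". Protocol 6.2.3 removes any doubt about which morning is meant: "Patients that complete the trial will take the last dose of study medication the day before Visit 98". Section 6.2.2 dispenses nothing at Visit 98. For early stoppers, section 3.3.4.1 asks for the Visit 98 "evaluations completed as soon after stopping study medication as possible". The same sentence describes Visit 98 as an assessment made on treatment or shortly after.

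**Imputing the stop date.** SAP 6.6 (missing dates and times) gives, as a general rule:
- Rule 1: "If an End of Treatment (EoT) visit is documented, it should be the date of the EoT visit (Visit 98".
- Rule 2, for a date that is "incomplete with only month and year and the EoT visit is missing, it should be the first day of the following month".
- Rule 3 covers patients lost to follow-up. Remaining cases go to the trial team individually.
- After any of the first three rules, "the post-treatment phase starts at the same day as the imputed drug stop date", instead of one day later.

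**What the stop date controls.** SAP 6.7 treats measurements as "on-treatment values if they have been obtained up to 7 days after study medication stop (inclusive", with FPG limited to 1 day. The stop or last-intake date also sets the end of the last visit window and the choice of the last visit's value (6.7), the hypoglycaemia cut-off for early stoppers (7.5.2), exposure (7.7) and adverse event assignment (7.8.1).

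**The concern.** Under the protocol, nobody takes a tablet on the Visit 98 date. Rule 1 therefore imputes a date that is always too late: by one day for a completer, and by the whole interval between last tablet and visit for an early stopper. Rule 2 uses a recorded month and year only when Visit 98 is absent. A partial date with Visit 98 documented therefore appears to fall under rule 1, and the recorded month is lost.

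Two patients with the same history would then be classified differently only because one date is incomplete. Off-drug glucose values kept in the linagliptin arm pull it towards placebo. Events long after the last tablet are charged to randomised treatment, and exposure is inflated.

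**Working it through.** **Inputs.** On-treatment limits: stop + 7 days for HbA1c, stop + 1 day for FPG (SAP 6.7). Exposure = stop − start + 1 (SAP 7.7). Planned Visit 98 is Day 169 and Visit 99 is Day 176 (protocol flow chart). The number of missing stop dates and the gaps are not in the documents, so the gaps below are assumed.

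**Step 1: early stoppers.** Let g = Visit 98 day − last-tablet day. With the true stop date, HbA1c at Visit 98 is on-treatment if g ≤ 7, and FPG if g ≤ 1. With the stop date set to Visit 98, the gap becomes 0 and both always qualify.

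| g (days) | HbA1c, true stop | FPG, true stop | Both, imputed stop | Excess exposure (days) |
|---|---|---|---|---|
| 1 | on | on | on | 1 |
| 2 | on | off | on | 2 |
| 7 | on | off | on | 7 |
| 8 | off | off | on | 8 |
| 11 | off | off | on | 11 |
| 42 | off | off | on | 42 |

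The adverse event window also ends g days late. So does the hypoglycaemia limit, whether one takes stop + 7 (SAP 6.7) or the stop date itself (SAP 7.5.2).

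**Step 2: the compensating rule.** Starting the post-treatment phase on the imputed date takes one day off the treatment interval, leaving it g − 1 days too long. It is exactly right for completers only. SAP 6.6 does not extend it to the measurement windows or the exposure formula, and SAP 6.1.1 says the analysis rests on visit windows, not on those intervals.

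**Step 3: completers.** Last tablet Day 168, Visit 98 Day 169. Exposure is 169 days instead of 168. HbA1c and FPG status do not change, because g = 1. The +7-day safety limit moves from Day 175 (168 + 7) to Day 176 (169 + 7), the planned day of Visit 99. Japanese patients still on drug at Week 24 are not affected at that analysis, because their limits are fixed at Day 175 or 176.

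**Step 4: a recorded month.** Suppose the stop is recorded as March and Visit 98 is on 20 April. The true gap lies between 20 days (31 March) and 50 days (1 March). For every possible day in March, both HbA1c and FPG are off-treatment, yet rule 1 makes both on-treatment. If the last tablet was on 5 March, exposure is overstated by 46 days and the 7-day window ends on 27 April instead of 12 March.

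**Step 5: size for the primary endpoint.** The plan's power reproduces: 150 per arm, difference 0.77%, SD 1.2%, two-sided 5% t-test gives 99.98%, against the stated figure above 99%. As an assumed extreme, let 5 of 150 linagliptin patients contribute values that have lost the whole effect. The simple mean difference falls by 0.77 × 5/150 = 0.026 percentage points, or 3.3% of the effect. A 5% loss would leave power at 99.95%, and a 10% loss at 99.88%.

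**The case against.** The strongest reply is that Visit 98 is meant to happen promptly. The protocol itself treats it as on-treatment or shortly after, and SAP 6.7 already accepts HbA1c up to 7 days after the true stop. That stands for gaps of 7 days or less for HbA1c and 1 day for FPG. Beyond those limits, the SAP's own definition of on-treatment is bypassed.

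A reader might point to Protocol 4.3, where a patient with 10 tablet-free days is brought in for Visit 98, as proof of gaps of 10 + 1 = 11 days. The gap is real, but the documents do not support it as a typical case for this rule. SAP 7.3 has interruptions of more than 7 consecutive days recorded in the eCRF, so these patients are the least likely to lack a stop date. Category C3.3 in SAP Table 6.2: 1 also removes documented interruptions of 11 days or more from the per-protocol set.

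Other safeguards are partial. The observed-cases rule drops values after rescue, new antidiabetic therapy or a metformin or alpha-glucosidase inhibitor increase, and new therapy may start the day after stopping. A patient who simply stops the tablets keeps the value. The completers set excludes premature discontinuers, but it is only a sensitivity analysis.

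It is also fair to say that no rule expressly covers a partial date with Visit 98 documented. That the recorded month is overridden is an inference from rules 1 and 2 together. It is the natural reading, and the wording should settle it.

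**Conclusion.** The point holds as a defect in an imputation rule. For a premature discontinuer with a missing or incomplete stop date and a documented Visit 98, an off-drug FPG is counted as on-treatment at g ≥ 2 and an off-drug HbA1c at g ≥ 8, unless the observed-cases rule has already removed it. Exposure, the adverse event window and the hypoglycaemia cut-off are g days too long. For completers the shift is one day.

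A reader might infer that off-drug values of early stoppers in general enter the analysis, or that the primary result is at risk. The documents support neither. The rule touches only patients whose stop date is not fully recorded, and their number is not given. An early stopper's Visit 98 before Day 149 is assigned to an earlier visit (SAP Table 6.7: 1), so it reaches the Week 24 contrast only through the repeated-measures model. Protocol 3.2 says HbA1c reflects the preceding 12 weeks, so losing the whole effect in step 5 is an upper bound. For efficacy the expected bias is towards no difference. The effect on the primary result is likely very small. The case for changing the rule is consistent classification at almost no cost.

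**What to change.** Amend rule 1 in SAP 6.6 before unblinding:
- The imputed stop date never falls outside a recorded month and year, and is never later than the day before Visit 98.
- Completers: Visit 98 minus 1 day. The rule that starts the post-treatment phase on the imputed date then no longer applies to rule 1 and should be limited to match.
- Premature discontinuers: use recorded treatment interruptions (SAP 7.3) and tablet accountability (Protocol 4.1.8) first. Use the day before Visit 98 only if neither exists.
- Add a sensitivity analysis that excludes Visit 98 HbA1c and FPG values resting on an imputed stop date. The fallback still counts them as on-treatment, and this analysis shows whether that matters.

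The SAP's midpoint rule for other incomplete dates should not be borrowed. If the last in-clinic dose was L days before Visit 98, the midpoint between that dose and the day before Visit 98 lies (L + 1)/2 days before the visit. That exceeds 7 days once L ≥ 14 and 1 day once L ≥ 2. At the planned 42-day visit spacing it is 21.5 days. Genuine on-treatment values would be discarded.

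The cost is a few lines of SAP text, a small programming change and one extra sensitivity run. All the data needed are already to be collected. A few Visit 98 values may leave the observed-cases analysis.
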